9.2.3.2 Safety

Safety will be analyzed through the reporting of AEs. All AEs will be classified by body system and preferred term according to MedDRA dictionary. The severity of AEs will be classified using the

specific grading scale for allergic reactions associated with study procedures related to administration of peanut flour or placebo which was adapted from the CoFAR3 protocol (DAIT/NIAID IND # 13239). The NCI-CTCAE toxicity scale will be used for all other AEs. The total number of events and the number of participants experiencing AEs will be summarized by body system and preferred term for each treatment group and overall. Separate summaries will be provided for serious AEs, treatment-related AEs, and AEs leading to study discontinuation. Abnormal vital signs, physical examination results, and laboratory values that the investigator deems clinically significant will be graded according to the NCI-CTCAE toxicity scale and reported as AEs. Rates of withdrawal from therapy will be compared in the ITT, per protocol and safety samples.

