3.3.2 Secondary Endpoints

Efficacy:

1. Tolerance Endpoint
The proportion of participants who pass both the blinded OFC to 10 g peanut flour (5 g peanut protein) and the Open OFC to 8 g peanut protein in natural food form at week 160.
Passing a blinded OFC is defined in [Section 3.3.1](#).
Passing an Open OFC is defined in Section 6.4.3.
2. Transient Desensitization Endpoint
This is the change in proportion of participants who pass the blinded OFC to 10 g peanut flour (5 g peanut protein) at week 134 and week 160.
Passing a blinded OFC is defined in [Section 3.3.1](#).
3. Highest Tolerated Cumulative Dose Endpoint
The highest tolerated cumulative dose of peanut protein during the blinded OFCs will also be collected and analyzed.

Safety:

1. The incidence of all adverse events.
2. Rates of withdrawal from OIT or placebo.

Mechanistic:

Changes in the following markers of immune mediation:

1. Secreted cytokines
2. Anti-peanut IgE, IgG, IgG4 and secretory IgA
3. Epitope arrays
4. IgE-facilitated, CD23-dependent allergen binding to B cells
5. Serum, stools, and saliva assays
6. PBMC expression of transcription factors and cytokines relevant to food allergy

7. CD4+ CD25+ FoxP3+ Tregs
8. DNA-HLA genotyping
9. Peanut-specific T cells
10. Ara h 1 and Ara h 2 reactive T cells
11. Th2A Subset Analysis Basophil activation
12. B cells

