4.3 PREMATURE TERMINATION OF A PARTICIPANT FROM THE STUDY

Participants who prematurely terminate from the study will not be replaced.

Participants may be terminated from the study for the following reasons:

- The participant elects to withdraw consent from all future study activities, including follow-up.
- The participant is “lost to follow-up” (i.e., no further follow-up is possible because attempts to reestablish contact with the participant have failed).

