5.2 DISCONTINUATION OF STUDY TREATMENT

Participants will be terminated from further allergen therapy for the following reasons:

- Severe anaphylaxis with hypotension secondary to OIT dosing or any peanut food challenge.
- Inability to reach 3 mg peanut flour (1.5 mg peanut protein) during the initial dose escalation.
- Inability to reach 500 mg (250 mg peanut protein) during the Build-up phase.
- Poor control or persistent activation of secondary atopic disease (e.g., AD, asthma).
- Development of eosinophilic gastrointestinal disease.
- Circumstances (e.g., concurrent illness, such as gastroenteritis) requiring missed home dosing of > 14 consecutive days.
- Non-adherence with home dosing protocol with excessive missed days, defined as 3 occasions on which more than 3 consecutive home doses of study medication are missed.
- Eosinophilic esophagitis.
- Severe adverse event other than anaphylaxis related to investigational product.

Further care will be provided according to the judgment and practice of the site investigator.

Any subject deemed to have severe symptoms and who receives aggressive therapy at any time per investigator's discretion, should be discontinued from further escalation and followed-up as appropriate.

Participants who cease therapy should be asked to complete all assessments listed for Discontinuation Visit in Appendix 2.

If study treatment is discontinued, the DAIT/NIAID Medical Monitor will be notified.

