9. STATISTICAL CONSIDERATIONS AND ANALYTICAL PLAN

9.1 ANALYSIS SAMPLES

- Intent-to-treat (ITT) sample: All subjects who are randomly assigned to treatment or placebo will comprise the ITT sample.
- Per-protocol sample for the primary endpoint: All ITT subjects who are also study-compliant through the maintenance phase and have an evaluable blinded OFC at the end of the maintenance phase. Compliance is defined as completion of the maintenance phase as described in [Section 6.7.4](#); than 3 occasions on which more than 3 consecutive home doses of study medication were missed; and less than 3 non-protocol specified ingestions of peanut-containing food within a year.
- Per-protocol sample for the secondary endpoint: All participants included in the per protocol sample for the primary endpoint who are compliant with peanut avoidance during the avoidance phase and have an evaluable blinded OFC at the end of the avoidance phase. Compliance is defined as completion of the avoidance phase as described in [Section 6.7.5](#) and less than 3 non-protocol specified ingestions of peanut-containing food within a year.
- As-treated sample: All evaluable subjects, analyzed according to the amount of peanut therapy received, regardless of their randomized assignment.
- Safety sample: All enrolled subjects who receive at least one dose of OIT or placebo. Participants in the safety sample will be analyzed according to the treatment they actually received, regardless of their randomized assignment.

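### Withdrawal from therapy is compared in a per-protocol sample where it is zero by definition, and the AE summaries have no table for events that end treatment rather than study participation

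*Combined protocol and SAP*

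**What the plan says.** Section 3.3.2 lists as the second safety endpoint "Rates of withdrawal from OIT or placebo". Section 9.2.3.2 gives its analysis: "Rates of withdrawal from therapy will be compared in the ITT, per protocol and safety samples".

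Section 9.1 defines the per-protocol sample for the primary endpoint as "All ITT subjects who are also study-compliant through the maintenance phase and have an evaluable blinded OFC at the end of the maintenance phase". It adds: "Compliance is defined as completion of the maintenance phase", pointing to Section 6.7.4, where maintenance is at least 104 weeks of daily dosing. The per-protocol sample for the secondary endpoint is a subset of the first. The safety sample is every enrolled child who received at least one dose.

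For adverse events, Section 9.2.3.2 plans: "Separate summaries will be provided for serious AEs, treatment-related AEs, and AEs leading to study discontinuation". It plans no corresponding summary for discontinuation of treatment.

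The protocol has separate lists for the two kinds of stop. Section 5.2 opens: "Participants will be terminated from further allergen therapy for the following reasons". Several of its reasons are adverse events, such as eosinophilic disease or a severe related event. Section 4.3, on leaving the study, gives two reasons, loss to follow-up and this one: "The participant elects to withdraw consent from all future study activities, including follow-up".

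**The concern.** There are two mismatches between the safety endpoint and its planned output.

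First, an outcome is to be compared in a sample whose entry condition is that the outcome did not occur. The result is fixed before any data arrive, and a reader of the report could take equal rates of zero as reassurance about tolerability.

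Second, the endpoint concerns stopping treatment, but the one discontinuation table concerns leaving the study. A child can stop dosing because of an adverse event and stay in follow-up. Read literally, the event that ended treatment is then not identified as such in any planned table. For a daily therapy in children aged 12 to under 48 months at entry, the reasons for stopping treatment are a main tolerability result.

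**Working it through.** **Plan's own figure.** The plan states no figure for withdrawal from therapy. Its one related calculation is the sample size in Section 9.3: 0.34 versus 0.1275 for tolerance, 2:1 allocation, two-sided 0.05, 80% power, Pearson chi-squared. With pooled variance and no continuity correction:

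- Pooled proportion = (2 × 0.34 + 0.1275)/3 = 0.2692.
- Placebo n = [1.960 × √(0.2692 × 0.7308 × 1.5) + 0.842 × √(0.34 × 0.66/2 + 0.1275 × 0.8725)]² / 0.2125² = 47.4, rounded up to 48.
- Total = 48 + 96 = 144, as stated. Power at that size is 80.6%.

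Nothing below alters this figure.

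**Per-protocol comparison.**

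1. Entry to the sample requires completion of maintenance (Section 9.1).
2. Maintenance is at least 104 weeks of daily dosing (Section 6.7.4).
3. After maintenance and the week-134 challenge, all dosing stops (Section 6.7.5). If that challenge is inconclusive, Section 6.4.4 continues the maintenance dose until a repeat; I read completion as covering this extension.
4. A child who withdrew from therapy fails step 1. A child who passes step 1 has no therapy left to withdraw from.
5. The number withdrawn is therefore 0 in each arm. The secondary per-protocol sample, being a subset, gives the same.

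The missed-dose part of the compliance definition is garbled in the text, but the result rests on the completion requirement alone.

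**What the other samples would show.** The documents give no withdrawal rates by arm. Section 9.3 assumes 15% dropout, but defines it as loss to follow-up, not as stopping therapy. The rates below are therefore assumptions. Counts are rate × 96 and rate × 48, rounded. The test is z = difference / √[p(1−p)(1/96 + 1/48)] with p the pooled proportion.

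| Assumed OIT vs placebo | ITT counts | Difference (points) | p | Per-protocol (largest possible n) |
|---|---|---|---|---|
| 15% vs 15% | 14/96 vs 7/48 | 0 | 1.0 | 0/82 vs 0/41 |
| 20% vs 5% | 19/96 vs 2/48 | 15.6 | 0.012 | 0/77 vs 0/46 |
| 25% vs 10% | 24/96 vs 5/48 | 14.6 | 0.040 | 0/72 vs 0/43 |
| 30% vs 10% | 29/96 vs 5/48 | 19.8 | 0.008 | 0/67 vs 0/43 |

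For the second row: p = 21/144 = 0.1458; standard error = √(0.1458 × 0.8542 × 0.03125) = 0.0624; z = 0.15625/0.0624 = 2.50. The last column does not respond to the assumed rates.

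**AE table.** No arithmetic applies; the question is what counts as leaving the study.

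- *Stopping therapy and leaving the study are distinct:* Sections 5.2 and 4.3 list different reasons. Section 6.7.3 takes children who cannot reach the minimum build-up dose off dosing but keeps them in longitudinal follow-up.
- *The two are blurred:* Section 6.1.3 mentions termination by investigator decision. Section 6.7.2 says that a child failing initial escalation does not remain in the study, although Section 5.2 lists the same event as a stop of therapy. Section 5.2 asks children who cease therapy to complete the discontinuation-visit assessments. Section 9.3 speaks of children who discontinue participation yet return for a challenge.

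The same child could thus be classified either way, and the share of treatment-ending events missing from the table cannot be derived from the text.

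**Source of the events.** Under Sections 8.2.2 and 8.3.2.2, expected, related reactions within two hours of dosing go on dosing-specific forms. They become AEs only if they meet listed criteria, such as hypotension or more than two epinephrine injections. A table built from AE forms alone would miss treatment stops caused by the remaining reactions, whatever its title.

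**The case against.** The strongest reply is that little is lost. The sentence in Section 9.2.3.2 names the ITT and safety samples, so the endpoint already has two informative analyses; an empty third one biases nothing and feeds no decision. This stands. A reader might infer that the withdrawal endpoint is not properly analysed, and the documents do not support that.

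A second reply is that Section 4.3 says participants may be terminated for the listed reasons, not that no others exist, and that other sections use study exit more broadly. This also stands. A reader might infer that the study-discontinuation table would be nearly empty while treatment stops are frequent. That needs a strict reading of Section 4.3 which Sections 6.1.3, 6.7.2 and 9.3 do not bear out. The loose usage is nevertheless a reason to define the term before tables are programmed.

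A third reply is that the adverse events are reported anyway. Events recorded as AEs appear in the overall summaries by arm, and where applicable in the serious and treatment-related ones. That is correct, so it would be wrong to say they go unreported. What is missing is the link from event to treatment stop. A withdrawal rate shows how many stopped but not which events led to it, and the other AE summaries show events but not which of them ended treatment.

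**Conclusion.** The point holds as a minor correction. The per-protocol withdrawal comparison is 0% versus 0% by construction, which needs no assumption about rates. It is uninformative, but the valid ITT and safety comparisons beside it are untouched.

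The missing table is a real gap against safety endpoint 2: the endpoint concerns treatment, the table concerns the study, and the protocol separates the two in Sections 5.2 and 6.7.3 against 4.3. Its size is unknown. It depends on how many children stop treatment because of an event, how many of them stay in follow-up, and how sites apply the term study discontinuation; the documents fix none of these. The scenarios shown are illustrations, not estimates. Sample size, power and the primary analysis are unaffected.

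**What to change.** In Section 9.2.3.2 and the matching table shells:

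1. Remove the per-protocol sample from the withdrawal comparison and keep the safety and ITT samples.
2. Add a summary by arm of events leading to discontinuation of study treatment, classified by Section 5.2 reason. Draw it from both the AE forms and the dosing-specific forms, so that reactions kept off the AE form under Sections 8.2.2 and 8.3.2.2 are included.
3. Report study exit separately with its own reasons, and state which of the uses in Sections 4.3, 6.1.3, 6.7.2 and 9.3 counts as exit for that table.

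The cost is a wording change and a little more table programming, with no new visits and no change to any clinical rule. It relies on the reason and date of each treatment stop being captured in the database, which should be confirmed first.

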9.2.3.3 Mechanistic

The mechanistic analyses of endpoints described in [Section 7](#) will be performed using a wide range of statistical methodologies. Generally, all statistical tests will be two-sided at the $\alpha = 0.05$ level of significance. Normality can be assessed by a combination of methods including graphical analysis (e.g. normal probability plots, histograms, and quantile-quantile plots) and formal hypothesis tests (e.g. Kolmogorov-Smirnov test and Shapiro-Wilk test). Depending on the distributions of the data, parametric or non-parametric statistical methods may be performed. Transformation methods may also be used prior to fitting models where the normality assumption is required.

T-tests (both paired and two-sample tests), ANOVA, and ANCOVA models can be used to compare mean values among groups of interest and across multiple time points. Pearson correlations coefficients can be used to compare continuous measurements when data are considered to be normally distributed. Analogous non-parametric methods such as the Wilcoxon Signed Rank Test, Mann-Whitney U Test, the Kruskal-Wallis Test, and Spearman's rank correlation coefficient can be used if the data are considered non-normal.

9.2.4 Missing Data

Dropout in this study is anticipated to be $\leq 15\%$ and equally distributed between the randomized groups. The main ITT analysis requires that missing data be imputed. As noted in [Section 9.2.2](#), any randomized subject without an evaluable blinded OFC will be considered a treatment failure. Thus, up to about 15% of subjects could have results imputed and therefore be designated as not desensitized and not tolerant.

If missing data are not equally distributed between groups, biases can be created. For example, if a significantly greater proportion of dropout occurs in the treatment arm, this arm will have a larger proportion of imputed treatment failures than the placebo arm. This imbalance could tend to underestimate a treatment effect. Conversely, if a significantly greater proportion of dropout occurs in the placebo arm, this could tend to overestimate a treatment effect.

These opposing hypothetical biases will be investigated by examining the distribution of missing data as well as the factors associated with them in blinded and unblinded reviews.

Optimistic and pessimistic imputation methods and sensitivity analyses data will be used to provide upper and lower bounds for potential bias. These will provide a measure of robustness of the treatment as it relates to the causes and consequences of missing data. More specific details of the imputation methods and sensitivity analyses will be specified in the SAP. Generally, a combination of Multiple Imputation methods for missing data will be used including for example: regression, propensity scoring, and/or Markov chain Monte Carlo methods.

9.2.5 Medical History

Medical history—including the existence of current signs and symptoms—will be collected for each body system.

9.2.6 Use of Medications

All medications taken by or administered to study participants beginning 30 days before enrollment and continuing throughout the study will be collected. All medications used will be coded according to the WHO drug dictionary. The number and percentage of participants receiving prior and concomitant medications/therapies will be presented overall and by medication class.

9.3 SAMPLE SIZE

Prior experience indicates that a high proportion of subjects in the group receiving peanut oral immunotherapy will achieve desensitization to peanut, whereas only a small proportion of those who receive placebo will outgrow their allergy and be considered desensitized. The effect sizes for the primary endpoint is thus likely to be large.

A main aim of this trial, however, is also adequately to assess the secondary endpoint related to tolerance. In this case there is more limited prior experience. It is less well-known what proportion of the treated group will be considered tolerant when assessed after the avoidance phase, but it is certainly less than the proportion that are likely to be desensitized. To assess this endpoint adequately, the sample size needs to be larger than it would be for assessment of the primary endpoint alone.

The drop-out rate in a previous peanut oral immunotherapy trial by [name] group was about 25%.¹⁵ Adverse reactions in this trial were seen mainly during the dose escalation phase. Since then, the peanut escalation regimen has been completed over a longer duration. We therefore estimate that the overall drop-out rate in the current trial will be 15%.

Sample size requirements were determined by calculating the total enrollment necessary to provide adequate power for the tolerance endpoint, allocating subjects to treatment and placebo arms in a ratio of 2:1. The power calculations were performed using a two-sample Pearson Chi-squared test of proportions at a two-sided 0.05 level of significance.

Assumptions:

- For subjects completing study therapy, the proportions in treatment and placebo arms achieving desensitization are estimated to be 0.90 and 0.15 respectively.
- For subjects completing study therapy, the proportions in treatment and placebo arms achieving tolerance are estimated to be 0.40 and 0.15 respectively.
- Overall dropout proportion, which is the total loss to follow-up, at any time from randomization to the 160-week blinded OFC, will be 0.15.
- Under the intent-to-treat principle, subjects who discontinue study participation, but return to perform the 134-week or 160-week blinded OFC, will be evaluated as belonging to the arm to which they were randomly assigned.
- Subjects who lack evaluable endpoint data will be considered treatment failures; that is, not desensitized and not tolerant.

Combining these assumptions, we compute an as-analyzed expected rate of tolerance in the treatment arm of $0.40 \times (1 - 0.15) = 0.34$, and in the placebo arm of $0.15 \times (1 - 0.15) = 0.1275$.

We similarly compute an as-analyzed expected rate of desensitization in the treatment arm of $0.90*(1-0.15) = 0.765$, and in the placebo arm of $0.15*(1-0.15) = 0.1275$.

To provide 80% power for the tolerance endpoint with these assumptions and calculations requires a sample size of 144, which is 96 in the treatment arm and 48 in the placebo arm. A consequence of this sample size, combined with a large estimated effect size, is that the power for the primary endpoint is greater than 99%.

9.4 REPORTING DEVIATIONS FROM THE ORIGINAL STATISTICAL PLAN

The principal features of both the study design and the plan for statistical data analysis are outlined in this protocol and in the statistical analysis plan (SAP). Any change in these features requires either a protocol or an SAP amendment, which is subject to review by the IND Sponsor, DSMB, the study sponsor(s), and the FDA. These changes will be described in the final study report as appropriate.

10. ACCESS TO SOURCE DATA/DOCUMENTS

The investigational sites participating in this study will maintain the highest degree of confidentiality permitted for the clinical and research information obtained from participants in this clinical trial. Medical and research records should be maintained at each site in the strictest confidence. However, as a part of the quality assurance and legal responsibilities of an investigation, the investigational sites must permit authorized representatives of the ITN, IND Sponsor, and FDA to examine (and to copy when required by applicable law) clinical records for the purposes of quality assurance reviews, audits, and evaluation of the study safety and progress. Unless required by the laws permitting copying of records, only the coded identity associated with documents or other participant data may be copied (and any personally identifying information must be obscured). Authorized representatives as noted above are bound to maintain the strict confidentiality of medical and research information that may be linked to identified individuals. The investigational sites will normally be notified in advance of auditing visits.

11. QUALITY CONTROL AND QUALITY ASSURANCE

The investigator is required to keep accurate records to ensure that the conduct of the study is fully documented. The investigator is required to ensure that all CRFs are completed for every participant entered in the trial.

The sponsor is responsible for regular inspection of the conduct of the trial, for verifying adherence to the protocol, and for confirming the completeness, consistency, and accuracy of all documented data.

The CRFs will be completed online via a web-based electronic data capture (EDC) system that has been validated and is compliant with Part 11 Title 21 of the Code of Federal Regulations. Study staff at the site will enter information into the electronic CRFs, and the data will be stored remotely at a central database. Data quality will be ensured through the EDC system's continuous monitoring of data and real-time detection and correction of errors. All elements of data entry (i.e., time, date, verbatim text, and the name of the person performing the data entry) will be recorded in an electronic audit trail to allow all changes in the database to be monitored and maintained in accordance with federal regulations.

